5.2 PATIENT DISPOSITION

The number of patients recruited in OLE study will be tabulated for each cohort (A, B, and C) by region, country, study site, and treatment arm. The FAS, safety-evaluable, HRCT-evaluable, pharmacokinetic (PK)-evaluable, pharmacodynamics (PD)-evaluable, PRO-evaluable populations, and survival population, including numbers of patients in each population will be summarized by cohort as applicable. Patient disposition (the number of patients treated and are ongoing at the end of study reporting period) will be tabulated by Cohorts A and B and the treatment arm. Premature treatment discontinuation and study discontinuation, as well as reasons for discontinuations, will be summarized for Cohorts A and B.

5.3 SAFETY ANALYSIS

The safety objective for this study is to confirm the long-term safety and tolerability of 10 mg/kg of zinpentraxin alfa administered Q4W via IV infusion plus standard of care (SOC) treatment, on the basis of the following endpoints:

- Incidence and severity of AEs, with severity determined according to the 5-point severity scale (National Cancer Institute Common Terminology Criteria for Adverse Events, Version 5.0 [NCI CTCAE, v.5.0])

- Incidence and severity of IRRs and other AEs of special interest (AESIs)
- Proportion of patients permanently discontinuing study treatment due to AEs
- Change from baseline in targeted clinical laboratory test results

Safety analyses will be based on patients from safety populations and grouped according to cohorts and the treatment groups described in Section 5.1.1.

Safety will be assessed through descriptive summary of exposure to study drug, seriousness and severity of AEs, and AESIs, changes in laboratory test results, death, discontinuation from study treatment, ECG and vital signs. These summaries will be produced for the entire study period, from the start of OLE period till the time of the snapshot or end of the study.

5.3.1 Extent of Exposure

Extent of exposure to study drug during OLE, will be summarized descriptively (mean, standard deviation, median, range, and proportions where appropriate) for the following measures:

- Number of patients exposed
- Treatment duration (weeks), measured from date of first administration at Baseline Day 1 of OLE phase till the date of the last treatment administration + 4 weeks or the date of the snapshot, whichever occurs first
- Study Duration (Weeks), measured from date of first administration at Baseline Day 1 of OLE phase till the date of the last safety assessment or the date of the snapshot, whichever occurs first
- Cumulative number of infusions = total number of non-zero infusions
- Cumulative volume of infusion received = total volume of non-zero infusions
- Number of missed infusions
- Number of patients receiving reloading infusions
- Number of infusion cycles, defined as either up to 3 loading or reloading infusion or 1 regular infusion

Exposure to concurrent use of pirfenidone and/or nintedanib will also be summarized descriptively by cohort and treatment group as defined in Section 5.1.1.

5.3.2 Adverse Events

All verbatim (“investigator-reported”) AE terms will be assigned a standardized term (the “Preferred Term [PT]”) and a superclass term using the most current version of the Medical Dictionary for Regulatory Activities (MedDRA) thesaurus terms, and adverse event severity will be graded according to NCI CTCAE v5.0 scale. A by-patient AE data listing including onset study day, duration, PT, treatment, severity, relationship to treatment, treatment for AE, action taken, and outcome will be provided.

All AEs, SAEs, AEs leading to death, AESIs, and AEs leading to study treatment discontinuation that occur during or after the first dose of study treatment (i.e., treatment emergent adverse events [TEAEs]) will be summarized by PT and severity grade as appropriate. An exacerbation or worsening of a pre-existing condition will be considered treatment-emergent only if the most extreme intensity is greater than the intensity at baseline (i.e., the intensity for a given AE increases and its end date is on or after the date of the first dose in the OLE study). For events of varying severity, the highest grade will be used in the summaries. Listings of AEs, SAEs, and AESIs will also be produced. Any non-treatment emergent SAEs, will also be listed separately (SAE occurring in Cohorts A, B, and C before or after the AE reporting period, as described in Protocol Section 5.4 and Protocol Section 5.7).

Number of patients with AE, number of AEs, cumulative incidence of AE as well as the AE rate per 100 patient-years exposure (defined as the number of events/total duration in the study multiplied by 100) will be calculated, along with the corresponding 95% confidence intervals (CIs) for the patient-years' rates of the SOC (exact based on the Chi-square distribution [Ulm 1990]).

Summary tables of the following will be provided for each cohort and the treatment groups as described in Section 5.1.1, including, but not limited to:

- AEs and SAEs of any grade
- AEs by highest NCI CTCAE grade
- Severe AEs (NCI CTCAE Grade 3 or above)
- AEs leading to death
- AEs leading to study treatment discontinuation
- AEs leading to drug interruption
- AEs leading to withdrawal from study
- Treatment related AEs and SAEs
- AESIs defined as follows:
 - Cases of potential drug-induced liver injury that include an elevated alanine aminotransferase (ALT) or aspartate aminotransferase (AST) in combination with either an elevated bilirubin or clinical jaundice, as defined by Hy's Law (see Protocol Section 5.4.)
 - Suspected transmission of an infectious agent by the study drug, as defined in Protocol Section 5.3.
 - Suspected IRR with NCI CTCAE Grade ≥ 2
 - Suspected anaphylactic or hypersensitivity reactions (all grades)
 - Acute or suspected exacerbation of IPF (all grades)

- Common AEs, i.e., those occurring in at least 5% of patients
- Suspected IRR (all grades)

Summaries of safety data by baseline concurrent anti-fibrotic therapy will be provided as appropriate.

Deaths and causes of death will be summarized and a listing of patients who died during the study will be provided.

Summaries of confirmed or suspected Coronavirus Disease 2019 (COVID-19) AEs and AEs associated with COVID-19 will also be provided.

A listing of all pregnancies will be presented.

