5.6.2 Summaries of Demographics and Baseline Characteristics

Unless otherwise specified, the baseline value for each variable will be considered for the assessment collected on baseline Day 1, prior to administration of first study drug during OLE period. For subjects in Cohort C directly recruited from Study WA42293, baseline will be Day 1, prior to administration of first study drug during double-blind period.

Demographic and baseline characteristics (including, but not limited to, age, sex, race/ethnicity, concomitant IPF medication use, comorbid illnesses, and pulmonary function) will be summarized overall for the FAS population and by cohort and treatment group (as defined in Section 5.1.1) using descriptive statistics as appropriate.

Compliance with study drug will be computed for each patient as the proportion of prescribed study drug actually taken for the safety population.

Proportions of patients taking each concomitant medication will be provided for the safety population.

Medical history will be summarized using summary statistics, reporting the proportion of patients with at least one medical condition and the total number of medical conditions based on the safety population.

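### SAP 5.3.2 dates the end of a worsening AE, not the worsening, so a parent-study severity peak could be counted as an open-label extension TEAE

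*SAP*

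**What the plan says.** SAP section 5.3.2 opens by taking TEAEs to be events "that occur during or after the first dose of study treatment". For a pre-existing condition it adds a test: the worsening is treatment-emergent "only if the most extreme intensity is greater than the intensity at baseline". The parenthesis that follows explains this as meaning that "the intensity for a given AE increases and its end date is on or after the date of the first dose" in the OLE study. On severity it adds: "For events of varying severity, the highest grade will be used in the summaries".

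These other places bear on the rule:

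- **Protocol 6.3.1** defines a TEAE so that the worsening itself falls on or after the first dose.
- **SAP 1** says that the SAP supersedes the protocol's analysis plan. **SAP Appendix 1**, which lists changes from the protocol, does not mention this one.
- **SAP 5.6.2** sets the general baseline: "the baseline value for each variable will be considered for the assessment collected on baseline Day 1", before the first OLE dose, unless otherwise specified.
- **Protocol 5.4.1** has AEs still ongoing from WA42293 transferred into the WA42294 AE form for Cohort B.
- **Protocol 5.4.5.4** keeps a persistent AE as one record, holding its initial grade and, if it worsens, its most extreme grade. It asks for the date on which an event became serious, but for no date of a grade change.

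**The concern.** Two windows are missing from the SAP rule. Neither the most extreme intensity nor the highest grade in the tables is confined to the OLE. The only date tested is the end of the AE, and any transferred AE that was ongoing on OLE Day 1 will pass that test.

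In Cohort B this opens a route for severity reached in the parent study to enter the OLE tables. For patients formerly on placebo, such a peak came before their first active dose in either WA42293 or this study. Confirming long-term safety is the study's safety objective. The outputs exposed are the TEAE counts, the table by highest CTCAE grade and the table of Grade 3 or higher events.

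The rates per 100 patient-years are exposed too. They are "defined as the number of events/total duration in the study multiplied by 100", and SAP 5.3.1 defines study duration as "measured from date of first administration at Baseline Day 1 of OLE phase till the date of the last safety assessment" (or the snapshot, if earlier). A worsening that happened in WA42293 would then be divided by time that starts only at OLE Day 1.

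**Working it through.** The plan states no figure to reproduce, because this is a classification rule. The check applies the rule to example grade histories and then to all possible ones.

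**Inputs.** The rule is from SAP 5.3.2 and the Day 1 baseline from SAP 5.6.2. The one-record structure is from Protocol 5.4.5.4 and the transfer from Protocol 5.4.1. The grade histories are illustrations. That the record keeps its WA42293 peak is an assumption.

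**Notation.** g0 = initial grade; p = worst grade before OLE Day 1; d = last grade before the first OLE dose; o = worst grade on or after that dose.

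- SAP test with the peak kept: max(p, o) > d, and end date on or after the first OLE dose. Grade shown: max(p, o).
- Protocol 6.3.1: o > d.

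**Example histories**

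| History | SAP test | Grade shown | Protocol 6.3.1 |
|---|---|---|---|
| 1, 3, 1 before Day 1; ongoing at 1 | 3 > 1: TEAE | 3 (worst OLE grade 1) | not a TEAE |
| 1, 3, 1 before Day 1; rises to 2 in the OLE | 3 > 1: TEAE | 3 (worst OLE grade 2) | TEAE, Grade 2 |
| 1 before Day 1; rises to 3 in the OLE | 3 > 1: TEAE | 3 | TEAE, Grade 3 |
| 1, 3 before Day 1; still 3 | 3 > 3 fails | none | not a TEAE |
| 1 throughout | 1 > 1 fails | none | not a TEAE |
| 1, 3, 1; resolved before Day 1 | fails on end date | none | not a TEAE |

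The first row is the over-count and the second the over-grade. The first row also meets the parenthesis: the intensity did increase, and the AE ended after the first OLE dose.

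**All histories.** With Grades 1 to 4, p ≥ g0, p ≥ d, o ≥ d and the AE ending in the OLE, there are 85 patterns: 55 with o > d and 30 with o = d.

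- Of the 30 with no OLE rise, 14 have a peak above both the initial and the Day 1 grade, so they pass however the increase is judged. Ten of these 14 would be shown as Grade 3 or higher with a worst OLE grade of 1 or 2.
- Another 6 of the 30 began at their peak and only eased. Their peak exceeds the Day 1 grade, but the intensity never increased, so the parenthesis arguably excludes them. The point does not rest on these.
- All 55 true worsenings pass (0 missed). In 15 of them p > o, so the grade shown exceeds the worst OLE grade.
- If the record restarts at the Day 1 grade, or the peak is limited to the OLE, 0 of 30 are wrongly counted and 0 of 55 missed.

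These counts give every conceivable path equal weight. They show what the rule admits and are not rates.

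**Effect per patient.** One misclassified patient moves an incidence row by 100/N percentage points. The size of Cohort B is not given. The 600–700 planned for all cohorts is an upper bound on N, so the shift is at least 100/700 = 0.14 to 100/600 = 0.17 points.

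**The case against.** The strongest reply is that the harm depends on a form design not shown in the documents. Protocol 5.4.1 says that ongoing AEs are transferred, not which grade fields come with them, and if records restart at Day 1 there is no error. This stands, and it limits the severity.

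Second, the intent is fairly clear. The lead sentence of SAP 5.3.2 confines TEAEs to the time from the first dose, SAP 5.3 runs the safety summaries "from the start of OLE period till the time of the snapshot or end of the study", and Protocol 5.4.5.9 speaks of worsening during the study. The phrase 'only if' also states a necessary condition, not a sufficient one. All of this supports an OLE-only reading. But the parenthesis is the only operational test the SAP gives for a worsening, and no text resets the peak, dates a grade change or limits the tabulated grade to the OLE.

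Third, no hypothesis tests are planned, and the by-patient listing shows onset day, duration and severity. A reader could pick out AEs that began before the OLE, but those listed items do not show when the peak occurred.

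A reader might also infer that the rule errs in both directions, missing true OLE worsenings, and that its two clauses contradict each other. The documents do not support that. SAP 5.3.2 names the intensity at baseline as the comparator, and SAP 5.6.2 puts baseline at OLE Day 1. Misses arise only if the parenthesis is detached from that clause and given the initial grade as its comparator.

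**Conclusion.** The wording defect is real and the point is minor. As written, the rule admits a rise that happened before the OLE, and nothing confines the tabulated grade to the OLE. The consequence is over-counting and over-grading in Cohort B. It requires that the AE is still ongoing on OLE Day 1, that the transferred record keeps its WA42293 peak, and that the SAP sentence is programmed as it stands.

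The documents do not settle the second condition. They also give neither the number of transferred AEs nor their grade histories, so the frequency cannot be computed and may be zero. It would go too far to conclude that the Cohort B tables will be wrong, or to read the pattern counts as proportions of events.

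**What to change.** Replace the parenthesis in SAP 5.3.2 with: *the AE's grade rises, on or after the first OLE dose, above its last grade before that dose*. State that TEAE severity is tabulated as the worst grade on or after the first OLE dose. For transferred AEs, take the last pre-dose grade from the WA42293 record, or query it at rollover where grade changes are not dated.

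The cost is one SAP sentence and one derivation, plus site queries on transferred AEs if grades are undated. Those queries are the larger part of the work and will be retrospective for patients already enrolled. The change brings the SAP back to the definition in Protocol 6.3.1.

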Given the longer duration of this proposed study, it is expected that there may be occasional dose interruptions. Repeat loading of PRM-151 will be required on the resumption of study treatment at Days 1, 3, and 5 if any dose of study drug is missed (see Section 4.3.2). This is to ensure adequate tissue exposure of PRM-151, given the estimated tissue half-life of PTX-2 (24–30 days, see the PRM-151 Investigator's Brochure for further detail).

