5.4.1 Adverse Event Reporting Period

Investigators will seek information on adverse events at each patient contact. All AEs, whether reported by the patient or noted by study personnel, will be recorded in the patient's medical record and on the Adverse Event eCRF.

After informed consent has been obtained but prior to initiation of study drug, only SAEs caused by a protocol-mandated intervention (e.g., invasive procedures such as biopsies, discontinuation of medications) should be reported (see Section 5.5.2 for instructions for reporting serious adverse events). For patients in Cohort A and B, all other medical occurrences that begin before the start of study treatment but after obtaining informed consent will be recorded on the General Medical History and Baseline Conditions eCRF, and not on the Adverse Event eCRF. Adverse events that are ongoing from study WA42293 for Cohort B patients will be transferred over from the WA42293 database in the WA42294 Adverse Event eCRF.

After initiation of study drug, all AEs will be reported until 8 weeks after the final dose of study drug.

Instructions for reporting AEs that occur after the adverse event reporting period are provided in Section 5.7.

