5.7 ADVERSE EVENTS THAT OCCUR AFTER THE ADVERSE EVENT REPORTING PERIOD

After the end of the adverse event reporting period (defined as 8 weeks after the final dose of study drug), all deaths, regardless of cause, should be reported through use of the Long-Term Survival Follow-Up eCRF.

In addition, if the investigator becomes aware of a serious adverse event that is believed to be related to prior exposure to study drug, the event should be reported through use of the Adverse Event eCRF. However, if the EDC system is not available, the investigator should report these events directly to the Sponsor or its designee, either by faxing or by scanning and emailing the paper Clinical Trial Serious Adverse Event/Adverse Event of Special Interest Reporting Form using the fax number or email address provided to investigators.

5.8 EXPEDITED REPORTING TO HEALTH AUTHORITIES, INVESTIGATORS, INSTITUTIONAL REVIEW BOARDS, AND ETHICS COMMITTEES

The Sponsor will promptly evaluate all serious adverse events and adverse events of special interest against cumulative product experience to identify and expeditiously communicate possible new safety findings to investigators, IRBs, ECs, and applicable health authorities based on applicable legislation.

To determine reporting requirements for single adverse event cases, the Sponsor will assess the expectedness of these events through use of the reference safety information in the document listed below:

- PRM-151 Investigator's Brochure

The Sponsor will compare the severity of each event and the cumulative event frequency reported for the study with the severity and frequency reported in the applicable reference document.

Reporting requirements will also be based on the investigator's assessment of causality and seriousness, with allowance for upgrading by the Sponsor as needed.

The suspected unexpected serious adverse reaction (SUSAR) reporting will be as per the national regulatory requirements in participating countries in accordance with the Sponsor's internal standard operating procedures.

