6.3.1 Adverse Events

Verbatim descriptions of TEAE will be coded using the most current version of the Medical Dictionary for Regulatory Activities (MedDRA) and adverse event severity will be graded according to NCI CTCAE v5.0 scale. A TEAE is defined as any new adverse event reported or any worsening of an existing condition on or after the first dose of study drug.

The incidence and observation time-adjusted rate will be summarized, as appropriate. In addition, separate summaries will be generated for serious adverse events, deaths, adverse events of special interest, and adverse events leading to discontinuation of PRM-151. Adverse events will be summarized by mapped term, appropriate thesaurus level, and toxicity grade.

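### SAP 5.3.2 classifies a drug-related SAE with onset more than 8 weeks after the last dose both as treatment-emergent and as non-treatment emergent, so late related SAEs may be missing from the counted tables

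*SAP*

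**What the plan says.** **What is tabulated.** SAP 5.3.2 summarizes AEs, SAEs and AESIs "that occur during or after the first dose of study treatment (i.e., treatment emergent adverse events [TEAEs]) will be summarized by PT" and severity grade. It then plans summary tables that include SAEs and treatment-related AEs and SAEs. Neither the definition nor the table list has an end date. Protocol 6.3.1 is equally open-ended: a TEAE is "any new adverse event reported or any worsening of an existing condition on or after the first dose of study drug".

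**What is set apart.** The same SAP paragraph adds: "Any non-treatment emergent SAEs, will also be listed separately (SAE occurring in Cohorts A, B, and C before or after the AE reporting period". For that period it refers to Protocol 5.4 and 5.7.

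**What the sites collect.**
- Between consent and first dose, Protocol 5.4.1 asks for "only SAEs caused by a protocol-mandated intervention".
- On treatment and shortly after: "After initiation of study drug, all AEs will be reported until 8 weeks after the final dose of study drug".
- After those 8 weeks, Protocol 5.7 asks for an SAE on the Adverse Event eCRF "if the investigator becomes aware of a serious adverse event that is believed to be related to prior exposure to study drug".
- Deaths after the window are handled differently: "all deaths, regardless of cause, should be reported through use of the Long-Term Survival Follow-Up eCRF".
- Pregnancy-associated SAEs go on the Adverse Event eCRF, and the pregnancy is followed to its end, with no relatedness condition (Protocol 5.5.3.1; see also 5.5.3.3 and 5.5.3.4).

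**The concern.** A label that normally marks events outside the drug's risk period is applied to SAEs that, for the most part, reach the database because an investigator suspected the drug. Apart from deaths and pregnancy-associated SAEs, relatedness is the condition for reporting an SAE after the window at all.

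The study's stated safety objective is long-term safety. The SAE and related-SAE tables are where a reader looks for delayed harm. If the label decides what enters those tables, a late related SAE appears only in a listing and in no count. If the definition decides, the same event is counted. At present the outcome depends on which of two sentences the programmer follows.

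**Working it through.** No sample size, rate or event figure is involved, so the check is a reconciliation of the texts.

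**Step 1: the boundary.** The AE reporting period ends 8 weeks after the final dose (Protocol 5.4.1 and 5.7).

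**Step 2: who lies beyond it.** Patients who stop treatment in Cohort A or B move automatically to Cohort C unless they withdraw consent (Protocol 3.1.1, SAP 1.2) and are contacted about every 6 months (Protocol 5.3.4). Sites can therefore learn of late events, and the SAP parenthesis names Cohort C. Patients who enter Cohort C directly from Study WA42293 receive no OLE dose and are outside the safety-evaluable populations of SAP Table 2.

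**Step 3: a worked case.** Take an SAE the investigator considers related, with onset 12 weeks after the last OLE dose, which is 12 − 8 = 4 weeks past the window.

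| Text | Classification | Where the event goes |
|---|---|---|
| Protocol 5.7 | Reportable because believed related | Adverse Event eCRF |
| SAP 5.3.2, TEAE definition | Treatment-emergent | SAE and related-SAE tables |
| Protocol 6.3.1 | Treatment-emergent | SAE summary |
| SAP 5.3, period covered | Within the period (OLE start to snapshot or end of study) | Safety summaries |
| SAP 5.3.2, parenthesis | Non-treatment emergent | Separate listing |

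The last row conflicts with the three above it, and nothing in the SAP ranks them.

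**Step 4: can the protocol break the tie?** Not safely. SAP 1 says its analyses supersede those in the protocol. SAP Appendix 1, which records changes to protocol-planned analyses, mentions only the healthcare-utilization objective, so no narrowing of the TEAE definition is declared either.

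**Step 5: the parts of the parenthesis that are sound.** SAEs before the first OLE dose, and SAEs in Cohort C patients who never received an OLE dose, are not treatment-emergent in this study. The conflict is confined to onset after the first OLE dose and beyond the reporting window.

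**Step 6: rates.** SAP 5.3.2 divides the number of events by total duration in the study and multiplies by 100. SAP 5.3.1 ends study duration at the last safety assessment or the snapshot. The study discontinuation visit falls 4 + 4 = 8 weeks after the last dose (Protocol 4.6.2 and Appendix 1), and Cohort C has no safety assessments. A post-window event would therefore enter the numerator with no matching person-time.

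**The case against.** **Exclusion is inferred, not stated.** The SAP says these SAEs will also be listed. It does not say they will only be listed, and nowhere does it remove them from a table. The open-ended definition, the whole-study coverage in SAP 5.3 and the absence of a cut-off on the related-SAE table all point toward counting them. This stands, and it limits the finding to a contradiction that permits exclusion. It does not remove the problem: the parenthesis is the only text that places post-window SAEs by name, and an event flagged non-treatment emergent would not pass a TEAE filter. The word also may mean no more than in addition to the other listings.

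**Separating late events is defensible.** Reporting after the window is passive, since it depends on the investigator becoming aware, and Step 6 shows that such events do not belong in the person-time rates. This stands too. It is a reason for a flag and a separate count, not for a label that contradicts the definition. Deaths and causes of death are summarized whatever the label (SAP 5.3.2).

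**Stronger readings the documents do not support.**
- A reader might infer that every post-window SAE other than a death has been judged related. Pregnancy-associated SAEs are an exception.
- A reader might infer that all late related SAEs are certain to be excluded, or that the reported incidence must be too low. Both require the parenthesis to override the definition, which the SAP does not say.
- A reader might take the 24–30 day tissue half-life in Protocol 3.3.1 as evidence that delayed harm is likely or that the window is too short. The protocol gives that figure to explain reloading after a missed dose: "This is to ensure adequate tissue exposure of PRM-151, given the estimated tissue half-life of PTX-2". No text links residual tissue level to late SAEs, and the figure does not size an effect on any table.

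**Conclusion.** The concern holds as an internal contradiction in SAP 5.3.2 that should be resolved before the safety tables are programmed. On the documents' own definitions, the non-treatment-emergent label is wrong for a related SAE with onset after the first OLE dose. If it is applied as written, such events may be missing from the SAE and related-SAE counts.

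The size is unknown. The documents give no expected number of post-window SAEs, and it may be small. The conclusion rests on two readings: that the summary tables are built on the TEAE flag, as the definition sentence implies, and that the parenthesis is meant to classify events as well as to describe a listing. It does not depend on any view of the 8-week reporting window, and no change to that window is proposed.

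**What to change.** In SAP 5.3.2:

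1. Restrict the non-treatment-emergent label to SAEs before the first OLE dose, SAEs in patients with no OLE dose, and post-window SAEs not assessed as related. Adjust the TEAE sentence to match, so that the paragraph holds one rule.
2. Count every SAE with onset after the first OLE dose that the investigator assesses as related in the SAE and related-SAE tables, whatever its timing.
3. Flag those with onset more than 8 weeks after the last dose, and show the counts with and without them.
4. Leave flagged events out of the rates per 100 patient-years, and say so in a footnote, because study duration ends at the last safety assessment and ascertainment after the window is passive.
5. Record the rule in SAP Appendix 1 if it differs from Protocol 6.3.1.

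The cost is a few sentences and one derived flag. The events are already on the Adverse Event eCRF, so no new data collection, reporting duty or clinical rule is needed. The remaining drawback is that the flagged counts come from passive reporting and cannot be read as a complete incidence; the with-and-without display makes that visible.

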5.4.5.4 Persistent or Recurrent Adverse Events

A persistent adverse event is one that extends continuously, without resolution, between patient evaluation timepoints. Such events should only be recorded once on the Adverse Event eCRF. The initial severity (intensity or grade) of the event will be recorded at the time the event is first reported. If a persistent adverse event becomes more severe, the most extreme severity should also be recorded on the Adverse Event eCRF. If the event becomes serious, it should be reported to the Sponsor immediately (i.e., no more than 24 hours after learning that the event became serious; see Section 5.5.2 for reporting instructions). The Adverse Event eCRF should be updated by changing the event from "non-serious" to "serious," providing the date that the event became serious, and completing all data fields related to serious adverse events.

A recurrent adverse event is one that resolves between patient evaluation timepoints and subsequently recurs. Each recurrence of an adverse event should be recorded as a separate event on the Adverse Event eCRF.

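### SAP 5.3.2 puts a Poisson 95% interval on adverse event rates that count every event, so the limits are too narrow wherever events cluster within patients

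*SAP*

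**What the plan says.** SAP 5.3.2 plans the number of patients with an adverse event, the number of events, the cumulative incidence, and "the AE rate per 100 patient-years exposure", which is "defined as the number of events/total duration in the study multiplied by 100". The numerator is therefore events, not patients. The interval for this rate is given as "95% confidence intervals (CIs) for the patient-years' rates of the SOC (exact based on the Chi-square distribution [Ulm 1990"]).

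Protocol 5.4.5.4 governs what enters the numerator: "Each recurrence of an adverse event should be recorded as a separate event on the Adverse Event eCRF". Protocol 5.4.5.3 also has severe or serious secondary events recorded separately from the event that led to them.

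SAP 5.3.2 tabulates adverse events by cohort and by treatment group in the parent study. SAP 5.6.6 analyses safety separately for first- and second-generation product. Neither document names a robust variance, an overdispersion adjustment or a first-event rate. SAP 2 states that no statistical tests are planned.

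**The concern.** The exact chi-square interval has its stated coverage when the total count is Poisson, that is, when its variance equals its mean. If some patients contribute several events to the same class and most contribute none, the total varies more than that and the interval is too short.

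Long-term safety is this study's first objective, and these are the only intervals that SAP 5.3.2 specifies. Readers will set rates for cohorts, parent-study groups and drug generations side by side and judge differences by the printed limits. The frequent classes, where the interval looks tightest, are also where the exact method has least spare coverage to absorb clustering.

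**Working it through.** **Inputs.** The rate definition and interval method are from SAP 5.3.2. The recurrence rule is from Protocol 5.4.5.4. The Phase II counts are from Protocol 1.3.1. The ratio of variance to mean of per-patient counts, φ, is not given for this trial, so it is an assumption and is shown as a range.

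**Step 1: the planned interval.** For D events in person-time T, the limits for the expected count are χ²(0.025; 2D)/2 and χ²(0.975; 2D+2)/2, each then multiplied by 100/T. For D = 16 they are 9.1 and 26.0.

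**Step 2: the nominal level.** Coverage is the summed probability of every D whose limits contain the true mean. With a Poisson total (φ = 1) it is at or above 95% at every mean tried, so the method delivers what it claims under its own assumption.

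**Step 3: clustering.** The same sum was taken with a negative-binomial total having the same mean and variance φ × mean. Coverage in %:

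| Expected events | φ = 1 | 1.1 | 1.25 | 1.5 | 1.69 | 2.6 |
|---|---|---|---|---|---|---|
| 2 | 98.3 | 97.8 | 97.0 | 95.8 | 94.9 | 92.0 |
| 4 | 96.0 | 95.1 | 93.6 | 91.1 | 89.3 | 81.5 |
| 5 | 98.0 | 97.3 | 96.3 | 94.5 | 93.1 | 87.0 |
| 6 | 96.3 | 95.3 | 93.8 | 91.3 | 89.5 | 81.4 |
| 9 | 95.7 | 94.6 | 93.0 | 90.3 | 88.3 | 79.6 |
| 10 | 97.5 | 96.8 | 95.6 | 93.5 | 91.9 | 84.5 |
| 16 | 95.6 | 94.5 | 92.8 | 90.0 | 88.0 | 79.1 |
| 1000 | 95.2 | 94.1 | 92.3 | 89.4 | 87.2 | 78.0 |

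Coverage saw-tooths at small counts because D is discrete. Over whole-number means up to 10 with φ of 1.25 or less, the lowest value is 93.0%, at 9 expected events. From 16 expected events it is below 95% at every φ tested from 1.1 up.

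**Step 4: why more events do not help.** In large samples coverage tends to 2Φ(1.96/√φ) − 1, which does not depend on the count. It is 93.8%, 92.0%, 89.0% and 86.8% at φ = 1.1, 1.25, 1.5 and 1.69.

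**Step 5: what Phase II shows.** The group size follows from 9 patients being 11.7%: 9/0.117 ≈ 77.

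- Related fatigue on PRM-151: 16 events in 9 patients. The most even split is seven patients with 2 events and two with 1, so the sum of squares is 30. The mean is 16/77 = 0.208 and the variance is (30 − 16²/77)/76 = 0.351, so φ = 1.69. This is the minimum. The most uneven split (one patient with 8, eight with 1) gives 4.35, but nothing in the documents supports it. A negative binomial fitted to 16 events and 9 affected patients gives about 2.6.
- Related cough on PRM-151: 7 events in 7 patients, φ = 0.92. PRM-151 infusion reactions: 2 in 2, φ = 0.99. Related fatigue on placebo: 3 in 3. None shows recurrence. One placebo patient did have 2 infusion reactions.

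At φ = 1.69 the Poisson standard error is too small by a factor of √1.69 = 1.30. For 16 events, log-scale limits are 16 × exp(±1.96 × √(1.69/16)) = 8.5 to 30.2, against 9.1 to 26.0.

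**Step 6: the alternative.** Let patient i have x_i events in time t_i, N be the number of patients and r = D/T. The patient-clustered standard error of log r is √[N/(N−1) × Σ(x_i − r t_i)²] / D. Simulated coverage with 77 patients and equal follow-up:

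| Expected events, φ | Exact | Robust alone | Robust if D > 5, else exact |
|---|---|---|---|
| 2, 1.5 | 95.6 | 76.4 | 97.2 |
| 3, 1.5 | 96.5 | 87.6 | 96.6 |
| 16, 1.5 | 90.1 | 94.1 | 94.1 |
| 30, 1.5 | 90.3 | 94.7 | 94.7 |
| 12, 1.69 | 88.5 | – | 91.6 |
| 12, 2.6 | about 80 | – | about 87 |

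The dip at 12 arises because the exact upper limit at D = 5 is 11.67, so every sample left on the exact method misses a true mean of 12. With zero events the robust method gives no interval, while the exact upper limit is 3.69 events.

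**The case against.** The strongest reply is that little depends on these intervals. The safety endpoints in SAP 5.3 are incidence, severity, discontinuation and laboratory change; the event rate is not among them, and no test is planned. Patient counts, cumulative incidence and a by-patient listing are reported as well, so recurrence will be visible. The protocol also limits multiple counting: persistent events are entered once (5.4.5.4), most secondary events go under their primary cause (5.4.5.3), and symptoms are replaced by one diagnosis (5.4.5.2). All of this stands and limits the consequence. It does not make the stated 95% correct where recurrences are counted.

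The second reply is that the evidence for clustering is thin: one related-event term in Phase II, not a class rate, beside three counts with no recurrence. That also stands. A reader might infer from the fatigue figures that intervals in this trial will cover 80% or less. The documents do not support that, because the ratio here is unknown and even the fatigue data fix only a minimum. Nor do they support a blanket claim that every interval falls short: mild clustering in small classes is largely absorbed by the exact method's conservatism.

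A reader might also infer that the denominator is undefined. SAP 5.3.1 does define two durations ("Treatment duration (weeks), measured from date of first administration at Baseline Day 1 of OLE phase" and "Study Duration (Weeks), measured from date of first administration at Baseline Day 1 of OLE phase"), but SAP 5.3.2 states the denominator as total duration in the study, which matches the second. Only the word exposure is out of place. Likewise SOC is introduced in "plus standard of care (SOC) treatment" as standard of care, while here it apparently means system organ class, since terms are assigned "and a superclass term using the most current version of the Medical Dictionary for Regulatory Activities (MedDRA) thesaurus terms". Both are wording points and do not bear on coverage.

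**Conclusion.** The point holds, conditionally. The planned interval is exact for a Poisson count, the rate counts all events, and recurrences enter the count by rule. Where events cluster, the printed limits overstate precision. At 16 expected events coverage runs from 94.5% (φ = 1.1) to 88.0% (φ = 1.69), and larger counts do not restore it. At 10 or fewer expected events with φ of 1.25 or less, coverage is mostly at or near 95%, with a low of 93.0%. Stronger clustering also reduces coverage in small classes, for example 89.3% at 4 expected events and φ = 1.69.

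The direction is certain wherever φ exceeds 1 and counts are not small; the size in this trial is unknown. The figures assume a negative-binomial total, and the Phase II ratios assume similar follow-up across patients. Point estimates, patient-level incidence and events that can occur only once per patient are unaffected. This is worth correcting in the SAP, but no endpoint or test depends on it.

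**What to change.** In SAP 5.3.2, for event-count rates with more than 5 observed events, compute the 95% interval from a patient-clustered (robust) variance on the log-rate scale. For 5 or fewer events, including zero, keep the exact chi-square interval with a footnote that it assumes no within-patient clustering. In the same sentence, define SOC and replace the exposure label with the duration in SAP 5.3.1 that is meant.

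The cost is SAP wording and a standard procedure on data already collected. Intervals for recurrent events become wider and one table carries two methods. Coverage stays under 95% near the switch: about 91.6% at 12 expected events and φ = 1.69 (exact alone 88.5%), and about 87% against 80% at φ = 2.6. In simulations with assumed follow-up of 0.2 to 2 years, the robust interval covered 93.3% to 95.6% with 500 patients. With 77 patients, about 8 or more expected events and the heaviest clustering tried, it covered only 88.9% to 92.3%. It is an improvement, not a full cure.
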